10.4. Randomization Procedures and the Randomization Visit (Visit 2)

All participants who successfully complete the Placebo Run-In Period with $\geq 75\%$ adherence to placebo tablets will be eligible for randomization to pemafibrate or placebo. The Randomization Visit (Visit 2) will involve collection of key medical, social, and anthropometric information from the participant, as well as a brief physical examination and collection of blood samples for the non-fasting lipid panel.

The following procedures will be performed at the Randomization Visit (Visit 2):

- Review inclusion and exclusion criteria and confirm eligibility
- Document complete medical history
- Document CV risk factors and alcohol use
- Review concomitant medication use
- Administer the EQ-5D-5L quality of life questionnaire
- Perform a physical examination (eg, general appearance, head and neck, chest and lungs, etc.)
- Collect vital signs (blood pressure, heart rate, body weight, waist circumference, and BMI [to be calculated])
- Perform a compliance check through unused Placebo Run-In tablet count
- Randomize participants and dispense study drug
- Collect a *non-fasting* blood sample for safety and efficacy assessments (see Appendix A in Section 21.1 for details): chemistry, hematology, lipids, and other tertiary exploratory parameters (Section 11.3)
- Collect a *non-fasting* blood sample for archiving (in countries and at sites where it is approved by the IRB/IEC/REC) and other regulatory authorities, as applicable
- Collect urine samples (for creatinine and microalbumin)
- Collect blood for serum pregnancy testing (WOCP only)
- Query participant and record any reported or observed SAEs
- Query participant and record any CV efficacy events (see Section 11.1 and Section 11.2 for definitions of efficacy events)

Randomization

The site investigator will use an interactive computer system for randomization. The randomization process will involve stratification by sex, prior history of CVD (primary vs. secondary prevention cohorts), and statin use at baseline, defined as those who are taking no statin at baseline or are statin intolerant compared to all others at the Screening/Enrollment Visit. No more than one-third of the study population will comprise participants without prior CVD (primary prevention cohort). The DSMB and Executive Committee (EC) will monitor participant profiles and may increase or restrict enrollment of certain subgroups to control this proportion.

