11.2. Monitoring for the Occurrence of Diabetes-Related Events and Parameters

New or progressive diabetic retinopathy is confirmed when medical records document use of retinal laser treatment, antivascular endothelial growth factor therapy, or vitrectomy due to development of and/or deterioration of diabetic retinopathy. Initial reports of diabetic retinopathy will be collected by querying the participant at each study visit.

New and or progressive diabetic nephropathy is confirmed by laboratory evidence of an increase in microalbumin/creatinine ratio to ≥ 30 mg/g among those without microalbuminuria at baseline, or categorical change from baseline albuminuria (normo-, micro-, or macroalbuminuria), doubling of creatinine from baseline, creatinine level > 6.0 mg/dL, eGFR <15 mL/min/1.73 m², or initiation of renal replacement therapy (dialysis or transplant), among all participants. Laboratory data obtained during safety laboratory collections will be used for laboratory values and participants will be queried at each study visit for initiation of renal replacement therapy.

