3.2.3. Tertiary Endpoints

Tertiary endpoints include microvascular endpoints (ie, diabetic retinopathy and diabetic nephropathy as defined below) as well as exploratory mechanistic studies evaluating differences in average achieved levels and change from baseline between pemafibrate and placebo arms in:

- Core lipid parameters (total cohort): TG, HDL-C, calculated and directly measured LDL-C, calculated VLDL-C and non-HDL-C, TC, ApoB, ApoE, and directly measured remnant cholesterol
- Advanced lipid parameters (total cohort): ApoA1, ApoC3, LDL-C by beta-quantification (preparative ultracentrifugation [PUC]), lipoprotein particles (nuclear magnetic resonance [NMR] size, concentrations, and subfractions), HDL-TG and LDL-TG by PUC, and directly measured small dense low-density lipoprotein cholesterol (sdLDL-C) and low-density lipoprotein associated TG (LDL-TG)
- Inflammatory and glycemic parameters (total cohort): High-sensitivity C-reactive protein (hsCRP), fasting glucose, hemoglobin A1c (HbA1c), and fibroblast growth factor-21 (FGF-21)
- Expanded exploratory lipid and non-lipid parameters (US/Canada subcohort): ApoA5, ApoB48, angiopoietin-like 3 (ANGPTL3), ANGPTL4, PCSK9 mass, cytokeratin-18 (CK-18), and type IV collagen

Microvascular endpoints will also be examined. These will include *diabetic retinopathy*, defined as use of retinal laser treatment, anti-vascular endothelial growth factor therapy, or vitrectomy due to development of and/or deterioration in diabetic retinopathy and blindness; and *diabetic nephropathy*, defined as an increase in microalbumin/creatinine ratio to > 30 mg/g among those without microalbuminuria at baseline, or categorical change from baseline albuminuria (normo-, micro-, or macroalbuminuria), doubling of creatinine from baseline, creatinine level > 6.0 mg/dL, estimated glomerular filtration rate (eGFR) < 15 mL/min/1.73 m², or initiation of renal replacement therapy (dialysis or transplant) among all participants.

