8.4. Analysis of the Primary Efficacy Endpoint

8.4.1. Primary Efficacy Analysis

The primary endpoint of the trial is the time from randomization to the first occurrence of any component of the clinical composite endpoint of nonfatal myocardial infarction, nonfatal ischemic stroke, cardiovascular death, and coronary revascularization.

Patients who do not have an event will be censored at withdrawal of consent, end of study, or death. The censor date will be the date of withdrawal of consent for follow-up, CSED or the subject's last assessment, or death, whichever comes first. The time to event/censoring in days will be derived as (Date of First Occurrence of Event/Censoring – Date of First Dose) +1. The primary analysis of the trial will use a likelihood ratio test based on a proportional hazards model stratified on sex, prior history of CVD, and statin use at baseline to test the null hypothesis of no association between assignment to active K-877 and the rate of the primary endpoint. All analyses will classify patients according to their randomized treatment assignment, i.e. according to the intention to treat principle, and will base evaluation of statistical significance on a two-sided test with level 0.05. The estimated relative hazard in the K-877 group compared to the placebo group with an accompanying 95% confidence interval will quantify the treatment effect. If this relative hazard is less than 1, then 100*(1-estimated relative hazard) will be defined as the percent reduction in hazard associated with K-877 treatment. Rates of occurrence of the primary endpoint will be defined as the total number of subjects who have this event in a treatment group per 100 person-years of follow-up. Estimates of the probability of the primary

```
Kowa Research Institute, Inc.
Statistical Analysis Plan – Protocol K-877-302 (PROMINENT)
```

endpoint by time after randomization within treatment groups will be based on the method of Kaplan and Meier.

Analysis will be implemented using the SAS® procedure PHREG as follows:

```
PROC PHREG DATA = ...;

CLASS TREATMENT (ref='2');

MODEL AVAL*CNSR(1) = TREATMENT;

STRATA SEX CVD STATIN;

HAZARDRATIO TREATMENT / ALPHA=0.05;

RUN;

where AVAL = time to event

TREATMENT = Randomized treatment group (pemafibrate and placebo)

CNSR = Censoring variable - 0 = Event, 1 = Censored

SEX = sex

CVD = prior history of CVD

STATIN = statin use at baseline
```

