where PCHG = percent change from baseline

TREATMENT = Randomized treatment group (pemafibrate and placebo)

BASELINE = baseline value

SEX = sex

CVD = prior history of CVD

STATIN = statin use at baseline
```

The time to event microvascular tertiary endpoints will be analyzed as outlined for the primary analysis. The other tertiary endpoints will be analyzed using MMRM method. Each model will include the endpoint result change from baseline at each study visit as the response variable and

```
Kowa Research Institute, Inc.
Statistical Analysis Plan – Protocol K-877-302 (PROMINENT)
```

study visit, randomization strata, baseline endpoint result, baseline result-by-study visit interaction, treatment, and treatment-by-study visit interaction.

Analysis using MMRM method will be implemented using the SAS® procedure MIXED as follows:

```
PROC MIXED DATA = ...;

CLASS VISIT SEX CVD STATIN TREATMENT SUBJID;

MODEL CHG = VISIT SEX CVD STATIN BASELINE BASELINE*VISIT

TREATMENT TREATMENT*VISIT / DDFM=KR;

REPEATED VISIT / SUBJECT = SUBJID TYPE=UN;

LSMEANS TREATMENT*VISIT / DIFF CL;

RUN;

where CHG = change from baseline at each study visit

TREATMENT = randomized treatment group (pemafibrate and placebo)

BASELINE = baseline value

SEX = sex

CVD = prior history of CVD

STATIN = statin use at baseline

VISIT = study visit

SUBJID = subject ID
```

If the MMRM model using an unstructured covariance matrix fails to converge with the default Newton-Raphson algorithm, the Fisher scoring algorithm will be used to provide initial values of the covariance parameters. In the rare event that none of the above methods yields convergence, a structured covariance, such as heterogeneous Toeplitz and Toeplitz structures, will be used to model the correlation among repeated measurements. In this case, the empirical option will be used because the sandwich variance-covariance estimator is asymptotically consistent.

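### The nephropathy model has no term for baseline albuminuria or creatinine: the test is valid but less efficient than the collected data allow, by an amount the documents do not fix

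*SAP*

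**What the plan says.** SAP 8.5 gives nephropathy no model of its own: "The time to event microvascular tertiary endpoints will be analyzed as outlined for the primary analysis". The primary analysis in SAP 8.4.1 is a "proportional hazards model stratified on sex, prior history of CVD, and statin use at baseline", tested by likelihood ratio. The code has treatment as the only covariate: "MODEL AVAL*CNSR(1) = TREATMENT".

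The endpoint (SAP 3.2.3) includes "increase in microalbumin/creatinine ratio to > 30 mg/g among those without microalbuminuria at baseline, or categorical change from baseline albuminuria". It also includes doubling of creatinine, creatinine above 6.0 mg/dL, eGFR below 15, and renal replacement therapy. No direction is given for the category change. Protocol 11.2 points to worsening: "New and or progressive diabetic nephropathy is confirmed by laboratory evidence".

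Urine albumin and creatinine are collected at the Randomization Visit (Protocol 10.4). Serum creatinine is in the chemistry panel at Visits 1 and 2 (Protocol Appendix A). Study drug starts the day after Visit 2 (Protocol 9.1), so both are true baseline values. The other tertiary endpoints are adjusted for their own baseline in the repeated-measures model of SAP 8.5, and the Group B lipid endpoints in the ANCOVA.

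**The concern.** The endpoint definition uses baseline albuminuria, but the model does not. Two normoalbuminuric participants at 3 and 25 mg/g who share sex, prior-disease and statin strata are given the same baseline hazard, although one is close to the 30 mg/g threshold and the other is far from it. In a Cox model, leaving out a strong predictor of a common event pulls the hazard ratio toward 1 and costs power, even in a randomized trial.

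This composite is the renal efficacy endpoint in the plan. A modest benefit or harm would be easier to miss than it need be. Baseline covariates chosen after unblinding would look data-driven, so the choice has to be made beforehand.

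**Working it through.** **1. The plan's own power figure.** The only one is for the primary endpoint. With two-sided alpha 0.05, 90% power and hazard ratio 0.834, Schoenfeld's formula gives 4 × (1.960 + 1.282)² / (ln 0.834)² ≈ 1276 events; Freedman's gives 1283. Protocol 14.2 states 1279, and 1279 × 1.019 = 1303.3, rounded up to 1304. The figure reproduces. Nothing comparable exists for nephropathy.

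**2. Why the form of adjustment matters.** Distance to the next threshold on the log scale, if only worsening counts:
- at 3 mg/g: ln(30/3) = 2.30
- at 25 mg/g: ln(30/25) = 0.18
- at 35 mg/g (already micro): ln(300/35) = 2.15

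With an assumed within-person log SD of 0.5, the first two are 2.30/0.5 = 4.6 and 0.18/0.5 = 0.36 SDs from an event. The participant at 35 has a higher ratio than the one at 25 but is much further from the next event. One linear log-ratio term across all participants cannot describe this. Category plus log ratio within category can, because within a category the distance is a constant minus the log ratio.

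**3. Simulation inputs.** From the documents: 10,000 participants, 1:1; the planned strata (2 × 2 × 2 = 8); two-sided 0.05 likelihood ratio test; urine at Months 4 and 12, then yearly; 5-year study with 3-year enrolment, so follow-up uniform on 2 to 5 years (mean 3.5); 20% women. Assumed: median ratio 8 to 30 mg/g, baseline log SD 0.8 to 1.5, within-person log SD 0.4 to 1.0, drift 0.05 per year, other renal events 0 to 3% per year and equal between arms, 4% in the no-statin or intolerant stratum. Treatment shifts were set so that the planned model's power spanned 37% to 91%. There were 600 to 800 runs per setting, and differences carry a Monte Carlo error of about 1 to 2 points.

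**4. Worsening-only endpoint.** Selected settings, power in %:

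| Median mg/g; log SD; within-person SD; other events per year | Planned | + category | + category and distance | Gain, last vs planned |
|---|---|---|---|---|
| 10; 1.0; 0.4; 0 | 64.2 | 64.8 | 79.7 | 15.5 |
| 18; 1.2; 0.5; 0 | 81.3 | 82.3 | 93.8 | 12.5 |
| 18; 1.2; 0.5; 3% | 76.3 | 79.8 | 91.8 | 15.5 |
| 18; 1.2; 1.0; 0 | 67.8 | 70.7 | 77.5 | 9.7 |
| 18; 0.8; 1.0; 0 | 72.2 | 79.7 | 82.3 | 10.1 |

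Over all 18 settings of this set, category plus distance gained 6.5 to 18.7 points and category alone −1.0 to +8.5. In five further settings, a single linear log-ratio term gained 0.1 to 2.1.

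Smaller runs used category as a stratum with log-ratio slopes in normo- and microalbuminuria. They kept macroalbuminuric participants and assumed 1% per year of other renal events. Power rose from 46% to 63%, 45% to 52%, 63% to 77% and 52% to 69%, gains of 17, 7, 14 and 17 points (250 runs each). A further set of 150 runs per setting gave about 11 to 18.

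**5. Dependence on prognostic strength.** A second model assumed proportional hazards given the baseline log ratio, with 5% to 45% of participants having an event:

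| Log hazard ratio per SD | Gain from adjustment (points) |
|---|---|
| 0.5 or less | 0.0 to 2.5 |
| 1.0 | 2.7 to 10.7 |
| 1.5 | 5.8 to 17.5 |
| 2.0 | 12.3 to 20.0 |

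**6. Change in either direction.** In five settings, category plus distance lowered power by 8.5 points (56.1% to 47.6%) to 29.2 points (70.2% to 41.0%). A separate run showed no gain (12% against 11%).

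**7. Validity.** Under no effect the planned model rejected in 3.9% of runs and the category-plus-distance model in 3.2%. With category strata and slopes, planned and adjusted models both rejected in 4.4%.

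**The case against.** A reader might infer a fixed loss of well over 5 points of power. The documents do not support that. They give no nephropathy event rate, ratio distribution, within-person variability, treatment effect or power target, so every nephropathy-specific input is assumed. A narrower set of 250-run simulations, counting threshold crossings only and leaving out macroalbuminuric participants, gave gains of 13 to 27 points. The nearest settings in the wider set (within-person SD 0.4 and 0.5, no other renal events) gave 8.3 to 16.1, so the upper figure should not be quoted.

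The sign of the gain depends on reading categorical change as worsening. Protocol 11.2 supports that reading, but SAP 3.2.3 does not state it. This objection stands, and the definition must be settled together with the model.

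The simulations simplify the composite. They treat other renal events as equal between arms, whereas Protocol 4.7.2 reports that mean creatinine rose with pemafibrate. The proposed creatinine covariate was not tested, so no gain is claimed for it.

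A reader might also infer that the plan ignores baseline albuminuria, or that its hazard ratio is biased. Neither holds. The endpoint is defined relative to baseline, and randomization makes the planned test valid. The marginal and conditional hazard ratios are different quantities, so attenuation is not an error. Protocol 14.4 and the SAP synopsis also plan covariate-adjusted Cox models, but for the primary endpoint and without naming the albumin/creatinine ratio or creatinine.

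Finally, no confirmatory claim rests on this endpoint: it is tertiary and outside the testing hierarchy of SAP 8.5.

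**Conclusion.** The point holds as one of efficiency. The planned nephropathy model omits a baseline measurement that helps decide who reaches the event, although it is collected and comparable terms are used for the other tertiary endpoints. If only worsening counts and the adjustment follows the threshold structure, the power gain under the assumed inputs is roughly 6 to 19 points. It is about 0 to 2.5 points if the ratio is weakly prognostic or enters as one linear term for everyone. It vanishes or reverses if improvement in category also counts as an event. These are ranges over assumptions, not a property of the plan. The consequence is minor, and the change is worth making because it uses data already collected.

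**What to change.** In SAP 8.5, before unblinding, give the nephropathy endpoint its own paragraph:
- state that a categorical change in albuminuria means worsening only;
- add baseline albuminuria category (normo, micro, macro) to the strata, with a further stratum for a missing baseline ratio;
- add the baseline log albumin/creatinine ratio, with a separate slope in each category, and baseline log creatinine as covariates;
- keep the currently planned model as a sensitivity analysis;
- note that the adjusted hazard ratio is conditional on baseline albuminuria.

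The cost is SAP wording and one changed PHREG call, with no new data. Strata rise from 8 to at most 8 × 4 = 32, and some will be sparse, so the text should say in advance what happens if the macroalbuminuria slope cannot be estimated.

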8.6. Summary of Reasons for Efficacy Non-Evaluability/Exclusion from Efficacy Analyses

Any subjects excluded from the per-protocol population (PP) will be summarized by treatment group and supported by an individual subject data listing providing the reason each subject was made unevaluable.

9. QUALITY OF LIFE ANALYSES

9.1. Summary of European Quality of Life-5 Dimensions 5 Level Questionnaire

For assessment of health related quality of life, the EQ-5D-5L will be used to generate summary indices. These will be analyzed using an MMRM that will include the EQ-5D-5L VAS Score change from baseline at each study visit as the response variable and study visit, randomization strata, baseline result, baseline result-by-study visit interaction, treatment, and treatment-by-study visit interaction.

The same SAS® procedure MIXED as stated in Section 8.5 for the analysis of the tertiary lipid endpoints will be used.

10. SAFETY AND TOLERABILITY

The safety analyses will be summarized for all subjects included in the Safety population by treatment group.

10.1. Overall Summary of Adverse Events

Any AE that occurs during the study is a study AE. Treatment emergent adverse events (TEAEs) are defined as AEs that started or worsened in severity on or after the first dose of study medication and prior to the last date of study medication + 30 days (inclusive). The overall incidence summary of all AEs will include the following:

- Number and percent of subjects with at least one TEAE;
- Number and percent of subjects with at least one TESAE;
- Number and percent of subjects with at least one severe TEAE;
- Number and percent of subjects with at least one drug related TEAE;
- Number and percent of subjects with at least one drug related TESAE;
- Number and percent of subjects with at least one TEAE leading to death;
- Number and percent of subjects with at least one TEAE leading to study drug interruption/discontinuation;

The information presented in this table is derived from the adverse event record and these results may differ from summaries that use the end of study record as the data source (e.g., subject accounting and disposition). This can occur when counting the number of discontinuations due to AE using data in the end of study record compared to the outcome in the AE record.

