
Secondary Analyses:

Secondary clinical endpoint analyses will follow the same outline as the primary analysis for time to event data. Secondary lipid efficacy endpoints will use analysis of covariance with adjustment for baseline measurements and imputation of missing values.

In addition to the above, an analysis of time to first occurrence of individual endpoints and an analysis of total events (evaluating time to occurrence of the first and all recurrent non-fatal MI, nonfatal ischemic stroke, coronary revascularization, or CV death) will be performed.

Additionally, as a prespecified secondary analysis, evidence of any genetic effect modification that may relate to pemafibrate and incident CV events will be evaluated. In particular, whether the effect of pemafibrate as compared with placebo on CV events differs according to known genetic polymorphisms in the PPARA gene (such as, but not limited to rs6008845) will be assessed.

Safety Analyses:

The safety population includes all participants who received at least 1 dose of study treatment. Participants will be analyzed according to their randomized treatment group, unless a participant inadvertently receives the incorrect drug during the entire study, in which case, the participant will be grouped according to the treatment actually received. Safety analyses will include comparisons of post-randomization laboratory values by treatment group and rates of SAEs and AEs by treatment group, both overall and within system organ class (SOC).

Planned Interim Analyses:

To preserve alpha and to minimize the likelihood of an inflated effect estimate associated with early stopping, preplanned efficacy analyses will occur only upon accrual of approximately 50% and 75% of the planned study primary endpoints. The design of the study, including evaluation of the implications of interim monitoring on study power, considered that stopping boundaries will be based on the Haybittle-Peto method. Inefficacy will be assessed at 30%, 50%, and 75% of endpoints, based upon the Linear 10% Inefficacy Boundary approach described by Freidlin, Korn, and Gray.

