12.2.7. Adverse Events of Special Interest

Adverse events of particular interest as they pertain to pemafibrate will include muscle-related AEs and liver disease. Adverse event forms will be used to collect additional relevant clinical

information at each study visit at which AEs will be assessed. Instructions for entry of these events will be provided in the eCRF Completion Guidelines.

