where Φ is the standard normal distribution function, and $\psi(\lambda)$ is defined as follows:

$$\Psi(\lambda) = \lambda^{2} \left\{ \frac{\lambda}{(\eta + \lambda)} \left[1 - \frac{\left[e^{\left(- (T_{f} - T_{r})(\eta + \lambda)} \right)} - e^{\left(- T_{f}(\eta + \lambda) \right)} \right] \right\}^{-1} \\ = \lambda(\lambda + \eta) / \left(1 - \frac{\left[exp\left(- (T_{f} - T_{r})(\lambda + \eta) \right) - exp\left(- T_{f}(\lambda + \eta) \right) \right]}{T_{r}(\lambda + \eta)} \right)$$

λ_e is the incidence rate in the pemafibrate group,

 Q_e is the proportion of the total participants in the pemafibrate group,

 λ_c is the incidence rate in the placebo group,

 Q_c is the proportion of the total participants in the placebo group,

 η is the loss to follow up rate,

 T_r is the recruitment duration,

T_f is the follow-up duration (also equal to the length of the study,

 Z_{α} is the standard normal deviate at level α , and

$$\bar{\lambda} = Q_e \lambda_e + Q_c \lambda_c = .5\lambda_e + .5\lambda_c$$

These power calculations are based on the Intent-to-Treat (ITT) population analyses. The actual duration of enrollment (3.0 years) was updated for assumptions. In our power calculations, we used a range of pemafibrate non-compliance from 10% (at time of enrollment closure) up to a conservative 17%, and also assumed that none of the placebo group will initiate pemafibrate therapy (drop-in). The impact of noncompliance on power can be evaluated from interpolation using Table 6. For example, if the true rate of major CV events in persons meeting eligibility criteria but not on pemafibrate is 4.5 per 100-person years, and fully compliant pemafibrate reduces this rate by 20%, we estimate a rate of the primary endpoint of 3.8 per 100 person-years in the pemafibrate group and 4.5 per 100 person-years in the placebo group allowing for a conservative pemafibrate non-compliance of 17%, using 3 year enrollment period, and 1% annual loss to follow-up. This would correspond to an observed 16.6% reduction in the active treatment group relative to placebo with the above noncompliance and drop-in rates. The proposed study would thus require about 5 years of follow-up (from first patient randomized to study termination) to have power above 90% to detect the anticipated effect on observed event rates and ITT analyses, as summarized in Table 6.

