6.3. Data Presentation Conventions

Continuous variables (eg, age) will be summarized using descriptive statistics (the number of subjects with available data, the mean, standard deviation (SD), median, and minimum and maximum). Categorical variables (eg, race) will be summarized using counts and percentages. Percentages will be calculated using the total subjects per treatment group.

The following conventions are applied to all data presentations and summaries.

- For continuous variables, all mean and median values will be formatted to one more decimal place than the measured value. Standard deviation values will be formatted to two more decimal places than the measured value. Minimum and maximum values will be presented with the same number of decimal places as the measured value.
- For categorical variables, the number and percentage of responses will be presented in the form XX (XX.X%) where the percentage is in the parentheses.
- Date variables will be formatted as DDMMMYYYY for presentation. Time is formatted in military time as HH:MM for presentation.
- Wherever possible, data will be decimal aligned.
- P-values, if applicable, will be presented to 3 decimal places. If the p-value is less than 0.001 then it will be presented as <0.001. If the rounded result is a value of 1.000, it will be displayed as >0.999.
- Unless otherwise stated, any statistical tests performed will use 2-sided tests at the 5% significance level.

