10.2.1. Summaries of Adverse Event Incidence Rates for All Subjects

Incidence of TEAEs will be presented by SOC and PT. Subjects will be counted only once at the SOC level and will be counted once for each applicable PT; multiple occurrences of the same preferred term for a subject will be counted only once. Subjects who experience more than one event within the same SOC are counted once at each preferred term level.

Supplementary tables will summarize the events with respect to the maximum severity observed for each preferred term and relationship to study medication.

10.2.2. Summaries of Adverse Incidence Rates for Serious Adverse Events (SAE), Adverse Event Dropouts, and Death

Adverse event incidence rates, by SOC and PT, will be summarized for subjects who report a non-fatal serious adverse event, discontinue treatment prematurely due to an adverse event, and

deaths. A listing will also be generated of premature discontinuations due to all causality. Individual data listings will support these tables in two forms:

- 1. Sorted by subject and all events at the preferred term level.
- 2. Sorted by preferred term and listing all subjects.

10.3. Total Duration of Therapy, Average Daily Dose, Maximum Daily Dose, Final Daily Dose of Study Medication, Compliance, and Study Drug Exposure

The duration of treatment will be summarized as a continuous measure and in a frequency distribution. The average daily dose, maximum daily dose attained at any time during the study, the final daily dose taken just prior to study termination, and compliance will also be summarized.

Subject months of drug exposure will be presented as cumulative summary statistics. The total number of days of treatment will be determined for each subject and then summed over all subjects. This total is divided by 30 days to estimate the months.

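### TEAE tables stop counting at last dose + 30 days but divide by all treated subjects, so if the arms stop drug at different rates, the arm that stops more looks safer than it is

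*SAP*

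**What the plan says.** SAP 10.1 opens the TEAE window at first dose and closes it "prior to the last date of study medication + 30 days (inclusive"). All seven rows of its overall table have the form "Number and percent of subjects with at least one TEAE" or a variant of it (serious, severe, drug-related, leading to death, and so on). SAP 6.3 fixes the denominator: "Percentages will be calculated using the total subjects per treatment group". In SAP 10.2.1, "Incidence of TEAEs will be presented by SOC and PT", and "Subjects will be counted only once at the SOC level and will be counted once for each applicable PT".

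SAP 10.3 summarises subject-months of drug exposure but attaches them to no event count. Neither document plans an AE rate per person-year, a time-to-first-AE analysis, or an overall table of all AEs to study end. The protocol synopsis promises "rates of SAEs and AEs by treatment group, both overall and within system organ class (SOC") without giving the unit of the rate.

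The data for such analyses will exist. Protocol 7.3 keeps participants who stop drug in visits and calls, with AE monitoring, to the Common Study End Date (CSED) Visit. SAP 10.1 itself classes any event during the study as a study AE, but gives that class no row.

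**The concern.** A subject who stops for good after three months contributes about four months of counted time. A subject who stays on drug contributes the whole of follow-up. Both add one to the denominator. If permanent stopping is equally common and similarly timed in the two arms, this cancels. If it is not, the crude percentages mix the risk of the event with time on drug, and the distortion favours whichever arm stops more.

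Unequal stopping is plausible here, in either direction. Protocol 7.3.1 lists laboratory criteria for permanent discontinuation, and Protocol 4.7.2 reports transaminase-related AEs more often on pemafibrate than on placebo in earlier studies. Against that, Protocol 8.2.1 has participants who need a fibrate stop study drug first, which could happen more often on placebo.

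The efficacy side of the same plan avoids the problem: SAP 8.1 divides subjects with events by years at risk, and Protocol 14.4 reports per 100 person-years. At stake is whether the main AE comparison can be read at face value after several years of treatment.

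**Working it through.** **The plan's own figures.** The documents give no numerical target for AEs. The stopping input comes from Protocol 14.2: "we used a range of pemafibrate non-compliance from 10% (at time of enrollment closure) up to a conservative 17" per cent. It enters the power calculation as 20% × (1 − 0.17) = 16.6%, which is the stated effect. The event target also reproduces (1279 × 1.019 = 1303.3, rounded up to 1304), but nothing below depends on it.

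**Inputs**
- Follow-up T = 3.5 years (protocol synopsis, sample size). Protocol 6.1 says about 4 years; the ratios then change by no more than 0.002.
- Lag l = 30/365.25 = 0.082 years (SAP 10.1).
- Pemafibrate stopping d = 17% (Protocol 14.2).
- Placebo stopping: not in the documents. Assumed range 0% to 17%.
- AE rate λ, equal in both arms: assumed 1, 5 and 20 per 100 person-years.
- Further assumptions: constant AE hazard, stopping independent of AE risk, no restart.

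**Formulas.** A subject's window is W = min(stop time + l, T), and the crude TEAE percentage is the mean of 1 − e^(−λW).
- *Stopping spread over follow-up:* constant stopping hazard g = −ln(1 − d)/T, mean window l + (1 − e^(−g(T − l)))/g. For d = 17%, g = 0.0532 and the mean window is 0.082 + (1 − e^(−0.0532 × 3.418))/0.0532 = 3.21 years.
- *All stopping at 3 months (early bound):* crude risk (1 − d)(1 − e^(−λT)) + d(1 − e^(−λ × 0.332)). For d = 17% and λ = 0.05: 0.83 × 0.1605 + 0.17 × 0.0165 = 13.61%.

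**Results, λ = 5 per 100 person-years, no true difference**

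| Stopping, pemafibrate vs placebo | Pattern | Mean window (years) | Crude TEAE | Ratio |
|---|---|---|---|---|
| 17% vs 17% | spread | 3.21 vs 3.21 | 14.75% vs 14.75% | 1.00 |
| 17% vs 10% | spread | 3.21 vs 3.33 | 14.75% vs 15.30% | 0.964 |
| 17% vs 10% | 3 months | 2.96 vs 3.18 | 13.61% vs 14.61% | 0.931 |
| 17% vs 0% | spread | 3.21 vs 3.50 | 14.75% vs 16.05% | 0.919 |
| 17% vs 0% | 3 months | 2.96 vs 3.50 | 13.61% vs 16.05% | 0.847 |

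Across the three AE rates, 17% vs 10% gives 0.963 to 0.968 (spread) and 0.930 to 0.933 (early). For 17% vs 0% the ranges are 0.917 to 0.926 and 0.846 to 0.852.

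**A true 10% excess on pemafibrate** (λ = 0.055 vs 0.05). With no stopping in either arm the crude ratio would be (1 − e^(−0.1925))/(1 − e^(−0.175)) = 17.51%/16.05% = 1.09. At 17% vs 10% it is 16.09%/15.30% = 1.05 (spread) or 14.84%/14.61% = 1.02 (early). At 17% vs 0% it is 1.00 (spread) or 0.92 (early).

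**After the fix.** First events per person-year inside the window give a ratio of 1.00 in every equal-hazard row, as do all events counted to CSED.

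**The case against.** The strongest reply is that the TEAE tables are only part of the safety output and that the effect is small and conditional. Most of this stands, and it limits the point.

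- *A reader might infer that the plan drops all AEs later than 30 days after last dose.* The documents do not say so. SAP 10.2.2 states no treatment-emergent window for non-fatal SAEs, AE discontinuations and deaths; its window is unstated, not closed at 30 days. SAP 8.5 analyses all-cause mortality, and the clinical and microvascular endpoints, as time to event. Protocol 11.1 collects the clinical endpoints to CSED on or off drug.
- *A reader might take 17% non-compliance as 17% of the window lost.* That gives 0.83 × 3.5 + 0.082 = 2.99 years against 0.90 × 3.5 + 0.082 = 3.23, a ratio of 0.93, and 0.88 if placebo is 5%. It amounts to every stopper leaving at day 0. SAP 4.3.1 describes non-compliance as a share of participants who discontinue. With stopping spread over follow-up, the windows at 17%, 10% and 5% are 3.21, 3.33 and 3.42 years, and the ratios about 0.96 and 0.94.
- *Restarts.* Protocol 7.3 generally treats discontinuations as temporary. The window closes at the last dose, so an interruption followed by restart removes no time. Only permanent stopping matters.
- *Counting of the event that causes stopping.* It is still counted.
- *Visibility.* Duration of treatment (SAP 10.3), TEAEs leading to interruption or discontinuation (SAP 10.1) and dropout plots (SAP 7.1) would help reveal an imbalance. Seeing it does not correct the percentages.
- *Muscle and liver events.* Protocol 12.2.7 says "Adverse events of particular interest as they pertain to pemafibrate will include muscle-related AEs and liver disease", and SAP 10 has no grouped table for them. That is a separate gap in detail, partly covered by the preferred-term tables and by the laboratory summaries in SAP 10.5. It does not support the present point.

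**Conclusion.** The point holds for the TEAE tables in SAP 10.1 and 10.2.1. As written, their percentages are biased toward the arm with more permanent stopping, and nothing in the plan adjusts for it.

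The size depends on a placebo stopping rate that the documents do not give. At an assumed 17% vs 10% it is a relative shift of about 3% to 7%. At the extreme of 17% vs 0% it is about 7% to 15%. With equal stopping it is nil. These figures assume a constant AE hazard and stopping unrelated to AE risk.

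It would go too far to say that a true excess would be hidden: a 10% excess still shows as 1.05 to 1.02 at 17% vs 10%, and is masked or reversed only at 17% vs 0%. Nor do the documents show which arm will stop more. This is an inexpensive improvement to the safety reporting; it does not show that the planned safety conclusions would be wrong.

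**What to change.** In SAP 10.1 and 10.2.1, add first TEAEs per 100 person-years at risk by arm. Person-time should end at the first event or at last dose + 30 days, whichever is sooner, and no later than the end of AE collection. Give a rate ratio with a 95% CI, and keep the crude percentages as a descriptive column.

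In SAP 10.2.2, state the counting window, and tabulate SAEs and deaths over all follow-up to CSED, on or off drug, by randomised arm.

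A person-year rate removes the distortion exactly only when the hazard is roughly constant. For events that cluster soon after starting drug it can tilt the other way, which is a further reason to keep the crude column and add the all-follow-up tables.

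The cost is SAP wording and a few more safety tables to produce and review. The data are already collected, and trial conduct does not change.
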